10.7.2.1. Handling of Missing and Partial Dates

10.8. Appendix 8: Values of Potential Clinical Importance

10.8.1. Laboratory Values

Haematology					
Laboratory Parameter	Units	Category	Clinical Concern Range		
			Low Flag (< x)	High Flag (>x)	
	Defined	Male		0.54	
Hematocrit	Ratio of	Female		0.54	
	· ·	Δ from BL	↓0.075		
	g/L	Male		180	
Haemoglobin		Female		180	
		Δ from BL	↓25		
Lymphocytes	x10 ⁹ / L		0.8		
Neutrophil Count	x10 ⁹ / L		1.5		
Platelet Count	x10 ⁹ / L		100	550	
While Blood Cell Count (WBC)	x10 ⁹ / L		3	20	

Clinical Chemistry					
Laboratory Parameter	Units	Category	Clinical Concern Range		
			Low Flag (< x)	High Flag (>x)	
Albumin	G/L		30		
Calcium	mmol/L		2	2.75	
Creatinine	umol/L	Δ from BL		↑ 44.2	
Glucose	mmol/L		3	9	
Potassium	mmol/L		3	5.5	
Sodium	mmol/L		130	150	

Liver Function				
Test Analyte	Units	Category	Clinical Concern Range	
ALT/SGPT	U/L	High	\geq 2x ULN	
AST/SGOT	U/L	High	\geq 2x ULN	
AlkPhos	U/L	High	\geq 2x ULN	
T Bilirubin	µmol/L	High	\geq 1.5xULN	
	µmol/L		1.5xULN T. Bilirubin	
T. Bilirubin + ALT		High	+	
	U/L	-	\geq 2x ULN ALT	

10.8.2. ECG

ECG Parameter	Units	Category	Clinical Co	oncern Range		
			Lower	Upper		
Absolute						
		H1	> 450	< 480		
Absolute QTc Interval	msec	H2	≥ 480	< 500		
		H3	≥ 500			
Absolute PR Interval	msec	L, H	< 110	> 220		
Absolute QRS Interval	msec	L, H	< 75	> 110		
Change from Baseline	Change from Baseline					
Increase from Baseline	m	H1	> 30	≤ 59		
QTc	msec	H2	≥ 60			

10.8.3. Vital Signs

Vital Sign Parameter	Units	Clinical Concern Range		
(Absolute)		Lower	Upper	
Systolic Blood Pressure	mmHg	< 85	> 160	
Diastolic Blood Pressure	mmHg	< 45	> 100	
Heart Rate	bpm	< 40	> 110	
Respiratory Rate	breaths/min	≤ 8	≥ 20	
Temperature	°C	≤ 35.5	≥37.8	

Vital Sign Parameter	Units	Clinical Concern Range				
(Change from Baseline)		Decrease		Decrease Increase		ease
		Lower	Upper	Lower	Upper	
Systolic Blood Pressure	mmHg	≥ 20	≥ 40	≥ 20	≥ 40	
Diastolic Blood Pressure	mmHg	≥ 10	≥ 20	≥ 10	≥ 20	
Heart Rate	bpm	≥ 15	≥ 30	≥ 15	≥ 30	

10.9. Appendix 9: Abbreviations & Trade Marks

10.9.1. Abbreviations

Abbreviation	Description
ADaM	Analysis Data Model
AE	Adverse Event
ALT	Alanine aminotransferase
A&R	Analysis and Reporting
AUC	AUC Area under the concentration-time curve
AUC(0-7)	Area under the concentration-time curve from time zero to 7 hours post first dose (TID dosing)
AUC(7-14)	Area under the concentration-time curve from 7 to 14 hours post first dose (TID dosing)
AUC(14-24)	Area under the concentration-time curve from 14 to 24 hours post first dose (TID dosing)
AUC(0-12)	Area under the concentration-time curve from 0 to 12 hours post first dose (BID dosing)
AUC(12-24)	Area under the concentration-time curve from 12 to 24 hours post first dose (BID dosing)
AUC(0-24)	Area under the concentration-time curve from time zero to 24 hours post first dose
AUC(0-t)	Area under the concentration-time curve from time zero (pre-dose) to last time of quantifiable concentration within a participant across all treatments
AUC(0-т)	AUC from 0 hours to the time of next dosing
BID	Twice a day
BMI	Body Mass Index
BP	Blood Pressure
CDISC	Clinical Data Interchange Standards Consortium
CI	Confidence Interval
Cmax	Maximum observed concentration
CPMS	Clinical Pharmacology Modelling & Simulation
CS	Clinical Statistics
CRF	Case Report Form
CSR	Clinical Study Report
C-SSRS	Columbia Suicide Severity Rating Scale
CTR	Clinical Trial Register
CV _b /CV _w	Coefficient of Variation (Between) / Coefficient of Variation (Within)
DBF	Database Freeze
DBR	Database Release
DOB	Date of Birth
DP	Decimal Places
eCRF	Electronic Case Record Form
ECG	Electrocardiogram
EMA	European Medicines Agency
FDA	Food and Drug Administration

Abbreviation	Description
FDAAA	Food and Drug Administration Clinical Results Disclosure Requirements
GSK	GlaxoSmithKline
IA	Interim Analysis
ICH	International Conference on Harmonization
IDMC	Independent Data Monitoring Committee
IDSL	Integrated Data Standards Library
IMMS	International Modules Management System
IP	Investigational Product
ITT	Intent-To-Treat
MMRM	Mixed Model Repeated Measures
PCI	Potential Clinical Importance
PD	Pharmacodynamic
PDMP	Protocol Deviation Management Plan
PK	Pharmacokinetic
PP	Per Protocol
PopPK	Population PK
QC	Quality Control
QTcF	Friderica's QT Interval Corrected for Heart Rate
QTcB	Bazett's QT Interval Corrected for Heart Rate
RAP	Reporting & Analysis Plan
RAMOS	Randomization & Medication Ordering System
SAC	Statistical Analysis Complete
SDSP	Study Data Standardization Plan
SDTM	Study Data Tabulation Model
SoA	Schedule of Activities
SOP	Standard Operation Procedure
ТА	Therapeutic Area
TFL	Tables, Figures & Listings
TID	Three times a day
Tmax	Time taken to maximum observed plasma drug concentration

10.9.2. Trademarks

Trademarks of the GlaxoSmithKline Group of Companies

HARP

Trademarks not owned by the GlaxoSmithKline Group of Companies

NONMEM

SAS

WinNonlin

10.10. Appendix 10: List of Data Displays

10.10.1. Data Display Numbering

The following numbering will be applied for RAP generated displays:

Section	Tables	Figures			
Study Population	1.1 to 1.23	N/A			
Safety	2.1 to 2.41	2.1 to 2.6			
Pharmacokinetic	3.1 to 3.10	3.1 to 3.8			
Section	Listi	ings			
ICH Listings	1 to 33 an	1 to 33 and 40 to 73			
Other Listings	34 to 39 ar	34 to 39 and 74 to 79			

10.10.2. Mock Example Shell Referencing

Non IDSL specifications will be referenced as indicated and if required example mock-up displays provided in Appendix 11: Example Mock Shells for Data Displays.

Section	Figure	Table	Listing
Study Population	N/A	N/A	N/A
Safety	N/A	SAFE_T1	SAFE_L1
Pharmacokinetic	N/A	N/A	N/A

NOTES:

 Non-Standard displays are indicated in the 'IDSL Shell' or 'Programming Notes' column as '[Non-Standard] + Reference.'

10.10.3. Deliverables

Delivery	Description
SAC	Final Statistical Analysis Complete

10.10.4. Study Population Tables

Study F	Study Population Tables						
No.	Population	IDSL / Example Shell	Title	Programming Notes	Deliverable [Priority]		
Part A	Cohort 1 – sing	gle ascending dos	e, 3-way crossover): Subject Disposition				
1.1.	Safety (Part A)	ES1A	Summary of Subject Disposition for the Subject Conclusion Record (Part A)	ICH E3, FDAAA, EudraCT Add footnote: Note: "Subjects" is used to refer to "Participants" in all data displays to reflect GSK display standards and CDISC SDTM/ADaM standards.	SAC		
1.2.	Safety (Part A)	SD1	Summary of Treatment Status and Reasons for Discontinuation of Study Treatment (Part A)	ICH E3	SAC		
1.3.	Safety (Part A)	ES4	Summary of Disposition at Each Study Epoch (Part A)	ICH E3	SAC		
1.4.	All Subject (Part A)	ES6	Summary of Screening Status and Reasons for Screen Failure (Part A)	Journal Requirements	SAC		
Part A	Part A (Cohort 1 – single ascending dose, 3-way crossover): Protocol Deviation						
1.5.	Safety (Part A)	DV1	Summary of Important Protocol Deviations (Part A)	ICH E3	SAC		

Study F	Population Tabl	es			
No.	Population	IDSL / Example Shell	Title	Programming Notes	Deliverable [Priority]
Part A	Cohort 1 – sing	gle ascending dos	e, 3-way crossover): Population Analysed		
1.6.	All Subjects (Part A)	SP1	Summary of Study Populations (Part A)	 IDSL Add the following footnotes: [1] Subjects are included in the Randomised population if they were randomly assigned to treatment in the study. [2] Subjects are included in the Safety population if they have been randomized and received at least one dose of study treatment. [3] Subjects are included in the Pharmacokinetic population if they are in the Safety Population and a pharmacokinetic sample was obtained and analysed. 	SAC
Part A	(Cohort 1 – sing	gle ascending dos	e, 3-way crossover): Demographic and Baseline Characteris	tics	
1.7.	Safety (Part A)	DM3	Summary of Demographic Characteristics (Part A)	ICH E3, FDAAA, EudraCT Do not include Weight (to be included in Vital Signs summary) Add Footnote: [1] For calculating age, birth date is imputed as June 30 in the year of birth.	SAC

Study F	Population Tabl	es			
No.	Population	IDSL / Example Shell	Title	Programming Notes	Deliverable [Priority]
1.8.	Randomised (Part A)	DM11	Summary of Age Ranges (Part A)	EudraCT Only include age ranges applicable to the study ('Adult (18-64 years)' and '>=65-84 years')) Please add footnote to say that randomised population=enrolled population.	SAC
1.9.	Safety (Part A)	DM5	Summary of Race and Racial Combinations (Part A)	ICH E3, FDA, FDAAA, EudraCT	SAC
Part A	(Cohort 1 – sing	gle ascending dos	e, 3-way crossover): Medical Conditions and Prior and Concor	nitant Medications	
1.10.	Safety (Part A)	MH1 / MH4	Summary of Current/Past Medical Conditions (Part A)	ICH E3 Separate summaries for Current & Past conditions, if collected.	SAC
1.11.	Safety (Part A)	CM1	Summary of Concomitant Medications (Part A)	ICH E3	SAC
Part A	Cohort 1 – sing	gle ascending dos	e, 3-way crossover): Exposure and Treatment Compliance	·	
1.12.	Safety (Part A)	EX5	Summary of Exposure to Study Treatment (Part A)	ICH E3 Total daily dose (mg) and number of days	SAC
Part B	(Cohorts 2, 3, 4	and 5 – repeat do	se, sequential-group): Subject Disposition		
1.13.	Safety (Part B)	ES1	Summary of Subject Disposition for the Subject Conclusion Record (Part B)	ICH E3, FDAAA, EudraCT	SAC
1.14.	Safety (Part B)	SD1	Summary of Treatment Status and Reasons for Discontinuation of Study Treatment (Part B)	ICH E3	SAC

Study I	Population Tabl	les			
No.	Population	IDSL / Example Shell	Title	Programming Notes	Deliverable [Priority]
1.15.	All Subjects (Part B)	ES6	Summary of Screening Status and Reasons for Screen Failure (Part B)	Journal Requirements	SAC
Part B	(Cohorts 2, 3, 4	and 5 – repeat do	se, sequential-group): Protocol Deviation	·	
1.16.	Safety (Part B)	DV1	Summary of Important Protocol Deviations (Part B)	ICH E3	SAC
Part B	(Cohorts 2, 3, 4	and 5 – repeat do	se, sequential-group): Population Analysed		
1.17.	Safety (Part B)	SP1	Summary of Study Populations (Part B)	IDSL Add the following footnotes: [1] Subjects are included in the Randomised population if they were randomly assigned to treatment in the study. [2] Subjects are included in the Safety population if they have been randomized and received at least one dose of study treatment. [3] Subjects are included in the Pharmacokinetic population if they are in the Safety Population and a pharmacokinetic sample was obtained and analysed.	SAC

Study F	Population Tab	les			
No.	Population	IDSL / Example Shell	Title	Programming Notes	Deliverable [Priority]
Part B	Cohorts 2, 3, 4	and 5 – repeat do	se, sequential-group): Demographic and Baseline Characterist	ics	
1.18.	Safety (Part B)	DM1	Summary of Demographic Characteristics (Part B)	ICH E3, FDAAA, EudraCT Do not include Weight (to be included in Vital Signs summary) [1] For calculating age, birth date is imputed as June 30 in the year of birth.	SAC
1.19.	Randomised (Part B)	DM11	Summary of Age Ranges (Part B)	EudraCT Only include age ranges applicable to the study ('Adult (18-64 years)' and '>=65-84 years'))	SAC
1.20.	Safety (Part B)	DM5	Summary of Race and Racial Combinations (Part B)	ICH E3, FDA, FDAAA, EudraCT	SAC
Part B	Cohorts 2, 3, 4	and 5 – repeat do	se, sequential-group): Medical Conditions and Prior and Conco	omitant Medications	
1.21.	Safety (Part B)	MH1 / MH4	Summary of Current/Past Medical Conditions (Part B)	ICH E3 Separate summaries for Current & Past conditions, if collected.	SAC
1.22.	Safety (Part B)	CM1	Summary of Concomitant Medications (Part B)	ICH E3	SAC
Part B	Cohorts 2, 3, 4	and 5 – repeat do	se, sequential-group): Exposure and Treatment Compliance		
1.23.	Safety (Part B)	EX1	Summary of Exposure to Study Treatment (Part B)	ICH E3 Total daily dose, cumulative actual dose and number of days.	SAC

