10.3. Populations for Analyses

For purposes of analysis, the following populations are defined:

Population	Description
Enrolled	All participants who sign the ICF
Safety	All randomized participants who take at least 1 dose of study treatment. Participants will be analyzed according to the treatment they actually received.
PK	The 'PK Population' is defined as subjects in the 'Safety' population for whom a PK sample was obtained and analyzed.

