4. ANALYSIS POPULATIONS

Population	Definition / Criteria	Analyses Evaluated
All Subjects	 Comprises of all participant who were screened and allocated a subject number. 	 Screen Failure Population Analysed.
Randomised	 All participants who were randomly assigned to treatment in the study. This population will be based on the treatment the participant was randomized to. 	Age ranges
Safety	 Comprises of all randomised participants who received at least one dose of study treatment. This population will be based on the treatment the subject was randomised to. 	 All other Study Population Safety
Pharmacokinetic	• Participants in the 'Safety' population for whom a pharmacokinetic sample was obtained and analysed.	• PK

Refer to Appendix 10: List of Data Displays which details the population used for each display. Note: All data displays (Tables, Figures & Listings) will use the term "Subject" which reflects CDISC and GSK Data Display Standards terminology.

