10.6.2. Study Population

Date of Birth

• Only the year of birth will be captured, and therefore the date of birth is then derived as follows: Year of birth = YYYY \rightarrow Date of birth = 30th June YYYY

Age

- - Calculated as the integer part of (date of screening date of birth)

Age = integer part (date of screening – 30th June YYYY) / 365.25.

• Birth date will be presented in listings as 'YYYY'.

Body Mass Index (BMI)

• Calculated as Weight (kg) / [Height (m) 2]

Treatment Compliance

Treatment compliance will be calculated based on the formula:

Treatment Compliance = Number of Actual Doses / (Planned Treatment Duration in Days * Frequency)

- Frequency is 2 for BID and 3 for TID. Treatment compliance could be greater than 100% if there are events of overdose. Cumulative compliance (since Day 1) at each visit will be calculated.
- Planned Treatment Duration is defined as 1 day in Part A in each period and 14 days in Part B.

Extent of Exposure

- Number of days of exposure to study drug will be calculated based on the formula: Duration of Exposure in Days = Treatment Stop Date – (Treatment Start Date) + 1
- Participants who were randomized but did not report a treatment start date will be categorised as having zero days of exposure.
- The cumulative dose will be based on the formula:

Cumulative Dose = Sum of (Number of Days x Total Daily Dose)

• If there are any treatment breaks during the study, exposure data will be adjusted accordingly.

205184

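### SAP Table 1.17 (Part B populations) is run on the Safety population and cannot show anyone randomised but undosed; the cumulative-dose formula and the Table 1.8 footnote also need correcting

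*SAP*

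**What the plan says.** **Population tables.** SAP 10.10.4 lists two tables on the same shell (SP1) with the same three footnotes. Table 1.6 ("Summary of Study Populations (Part A", closing bracket omitted) has All Subjects (Part A) in its population column. Table 1.17 ("Summary of Study Populations (Part B", closing bracket omitted) has Safety (Part B). Footnote [1] of both reads "Subjects are included in the Randomised population if they were randomly assigned to treatment in the study". SAP section 4 defines Safety as: "Comprises of all randomised participants who received at least one dose of study treatment".

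**Enrolled and Randomised.** Protocol 10.3 defines Enrolled as "All participants who sign the ICF". SAP Table 1 (section 2.1) replaces Enrolled with Randomised and describes this as a renaming to match internal guidance. The programming note for Table 1.8 (Part A age ranges) says: "Please add footnote to say that randomised population=enrolled population".

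**Cumulative dose.** SAP 10.6.2 gives "Cumulative Dose = Sum of (Number of Days x Total Daily Dose" (closing bracket omitted). Duration of exposure there is stop date minus start date plus one, in calendar days. The same section says exposure will be adjusted for treatment breaks, without giving a method. It assigns zero days of exposure to participants who were randomised but have no treatment start date. Table 1.23 (Part B exposure, on Safety) asks for: "Total daily dose, cumulative actual dose and number of days".

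**The concern.** A population summary exists to show how many people were randomised and how many of them reached each analysis set. If the table is first restricted to those who were dosed, it cannot show the loss between randomisation and dosing.

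This is a realistic case here. Protocol 7.2 allows randomisation on Day -1, before the first dose. The summary of changes for Amendment 02 records a temporary dosing hold, with Cohort 2 dosing not completed except in the two sentinel participants. Interrupted or unstarted courses are therefore the situation these displays should describe correctly.

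The hold also makes the dose formula worth checking, because a formula in whole days does not obviously give the dose received when dosing stops during a day.

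The footnote matters because Enrolled under the protocol includes screen failures. Protocol 6.4 defines those as people who consented but were not randomised. A reader of the report would be told that two different groups are the same.

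**Working it through.** **Design figures.** Planned cohort sizes are 12 + 12 + 3 × 14 = 66, which matches protocol 5.1. The highest daily dose is 3 × 240 = 2 × 360 = 720 mg, which matches protocol 8.1.1.

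**Step 1: Table 1.17.** Let N be the number randomised in a Part B cohort and u the number of those never dosed.

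- On All Subjects or Randomised, the Randomised row shows N.
- On Safety, it shows N − u, which is also the Safety row.

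For Cohort 2, assuming all 12 planned participants were randomised:

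| u (assumed) | Randomised row, run on Safety | Randomised row, run on All Subjects |
|---|---|---|
| 0 | 12 | 12 |
| 1 | 11 | 12 |
| 3 | 9 | 12 |
| 10 | 2 | 12 |

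The documents do not give u. A part-dosed participant has had at least one dose, is in Safety, and is counted correctly in either version.

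**Step 2: other Part B summaries.** Disposition Tables 1.13 and 1.14 are also on Safety. Table 1.15 is on All Subjects but covers screening status and screen failure, and a randomised person is not a screen failure. Table 1.19 is on Randomised but summarises age only. Listing 47 (subjects excluded from any population) is on All Subjects and would identify an undosed participant individually. The information therefore survives in a listing and in one denominator, but no Part B flow summary shows it.

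**Step 3: cumulative dose.** Take a participant with no breaks who stops on Day d after k of f daily doses of size D. Read Total Daily Dose as the planned dose.

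- Formula: d × f × D
- Dose taken: ((d − 1) × f + k) × D
- Excess: (f − k) × D, which is zero when the last day is complete (k = f)

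The largest excess (k = 1) is 2 × 120 = 240 mg at 120 mg TID and 2 × 240 = 480 mg at 240 mg TID. At 360 mg BID it would be 360 mg, but SAP 5.1 notes that the Cohort 5 dose level was not required. For 120 mg TID, stopping after the first dose of the day:

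| Stop day | Formula (mg) | Taken (mg) | Excess |
|---|---|---|---|
| 1 | 1 × 360 = 360 | 1 × 120 = 120 | 240/120 = +200% |
| 3 | 3 × 360 = 1,080 | 7 × 120 = 840 | 240/840 = +28.6% |
| 7 | 7 × 360 = 2,520 | 19 × 120 = 2,280 | 240/2,280 = +10.5% |
| 14 | 14 × 360 = 5,040 | 40 × 120 = 4,800 | 240/4,800 = +5.0% |

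A break followed by resumption is a different case. With a 3-day break in a 14-day course, the unadjusted figure would be 5,040 mg against 11 × 360 = 3,960 mg, but the SAP requires an adjustment for breaks. The Part A exposure table (1.12) does not ask for cumulative dose, so this step concerns Part B only.

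**Step 4: Enrolled against Randomised.** Protocol Enrolled = consented = randomised + consented but not randomised. SAP Randomised = randomised. The two are equal only if there are no screen failures, yet Tables 1.4 and 1.15 are planned to report them.

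**The case against.** The strongest reply is that these are clerical points with safeguards already in place. Table 1.17 keeps its Randomised footnote, so the Safety entry looks like a slip. The same list has others: Table 2.29 and Listing 62 are Part B displays labelled Safety (Part A). Undosed participants still appear in Listing 47 and in the denominator of Table 1.19. The dose formula is a sum and does not say that the daily dose is the planned one. Read with the Table 1.23 instruction, a part-dosed day could contribute only what was taken. Compliance already counts actual doses. The Enrolled change is disclosed in SAP Table 1, and screened participants are kept in All Subjects.

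Most of this stands as a limit on size. It does not remove the need to correct the text: a slip in the population column still produces the wrong row if programmed as listed, and a formula with two readings should have one. Disclosing a change as a renaming does not make the footnote true.

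A reader might infer more: that participants caught by the hold were in fact miscounted, part-dosed ones included, and that the primary safety results are therefore wrong. The documents do not support that. They do not say that anyone was randomised and left undosed, or that anyone stopped mid-day. Part-dosed participants are counted correctly in Table 1.17. Treatment breaks are already to be adjusted. Undosed participants do not belong in the Safety denominators.

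**Conclusion.** The point holds as a reporting correction with three parts.

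- Table 1.17 as listed understates the Randomised count by exactly the number randomised and never dosed. That number is unknown and may be zero. This follows from the definitions and needs no other assumption.
- The cumulative dose in Table 1.23 would be overstated only for a stop partway through a dosing day, and only if Total Daily Dose means the planned dose. The ceiling is 240 mg at 120 mg TID and 480 mg at 240 mg TID. The percentage is largest for very early stops and falls to +5.0% on Day 14. Stops after a complete day are correct. This part is an ambiguity to close rather than a demonstrated error.
- The Table 1.8 footnote conflicts with protocol 10.3 whenever there is at least one screen failure.

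The primary safety denominators, the sample size and the stated precision are unaffected.

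**What to change.** 1. Change the population of Table 1.17 to All Subjects (Part B), matching Table 1.6. Check the rest of the population column at the same time, including Table 2.29 and Listing 62.
2. Define cumulative dose in SAP 10.6.2 as the sum of doses actually administered. Protocol 7.5 has the date and time of each dose in the clinic recorded, and the compliance formula already needs the number of actual doses. This definition also handles treatment breaks without a separate rule.
3. Remove the footnote from Table 1.8. In SAP Table 1, describe the move from Enrolled to Randomised as a change of definition.
4. Delete the zero-days rule in SAP 10.6.2 or say where it applies. It cannot take effect in Table 1.23, which is on Safety.

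The cost is SAP wording and minor programming. No new data are needed.

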10.10.5. Safety Tables

Safety:	Tables				
No.	Population	IDSL / Example Shell	Title	Programming Notes	Deliverable [Priority]
Part A	(Cohort 1 – sing	gle ascending dos	se, 3-way crossover): Adverse Events (AEs)		
2.1.	Safety (Part A)	AE1	Summary of All Adverse Events by System Organ Class and Preferred Term (Part A)		SAC
2.2.	Safety (Part A)	AE5A	Summary of All Adverse Events by Maximum Intensity by System Organ Class and Preferred Term (Part A)	ICH E3	SAC
2.3.	Safety (Part A)	AE5A	Summary of All Drug-Related Adverse Events by System Organ Class and Preferred Term and Maximum Intensity (Part A)	ICH E3	SAC
2.4.	Safety (Part A)	AE15	Summary of Common (>=10%) Non-serious Adverse Events by System Organ Class and Preferred Term (Number of Subjects and Occurrences) (Part A)	FDAAA, EudraCT	SAC
Part A	(Cohort 1 – sing	gle ascending dos	se, 3-way crossover): Serious and Other Significant Adverse Ev	vents	
2.5.	Safety (Part A)	AE16	Summary of Serious Adverse Events by System Organ Class and Preferred Term (Number of Subjects and Occurrences) (Part A)	FDAAA, EudraCT Only if 3 or more SAEs reported	SAC
2.6.	Safety (Part A)	AE3	Summary of Adverse Events Leading to Permanent Discontinuation of Study Treatment or Withdrawal from Study by Overall Frequency (Part A)	IDSL	SAC
Part A	(Cohort 1 – sing	gle ascending dos	se, 3-way crossover): Laboratory: Chemistry	•	
2.7.	Safety (Part A)	LB1	Summary of Chemistry Changes from Baseline (Part A)	ICH E3	SAC
2.8.	Safety (Part A)	LB17	Summary of Worst Case Chemistry Results by PCI Criteria Post-Baseline Relative to Baseline (Part A)	ICH E3	SAC

Safety	Tables				
No.	Population	IDSL / Example Shell	Title	Programming Notes	Deliverable [Priority]
2.9.	Safety (Part A)	LB17	Summary of Worst Case Lipids Outside Laboratory Normal Range Post-Baseline Relative to Baseline (Part A)		SAC
Part A	(Cohort 1 – sing	gle ascending dos	se, 3-way crossover): Laboratory: Hematology	·	
2.10.	Safety (Part A)	LB1	Summary of Hematology Changes from Baseline (Part A)	ICH E3	SAC
2.11.	Safety (Part A)	LB17	Summary of Worst Case Hematology Results by PCI Criteria Post-Baseline Relative to Baseline (Part A)	ICH E3	SAC
Part A	(Cohort 1 – sing	gle ascending dos	se, 3-way crossover): Laboratory: Urinalysis		
2.12.	Safety (Part A)	UR1	Summary of Worst Case Urinalysis Results (Discrete or Character Values) Post-Baseline Relative to Baseline (Part A)	ICH E3	SAC
Part A	(Cohort 1 – sing	gle ascending dos	se, 3-way crossover): Laboratory: Hepatobiliary (Liver)	·	
2.13.	Safety (Part A)	LIVER1	Summary of Liver Monitoring/Stopping Event Reporting (Part A)	IDSL	SAC
2.14.	Safety (Part A)	LIVER10	Summary of Hepatobiliary Laboratory Abnormalities (Part A)	IDSL	SAC
Part A	(Cohort 1 – sing	gle ascending dos	se, 3-way crossover): ECG	·	
2.15.	Safety (Part A)	EG1	Summary of ECG Findings (Part A)	IDSL	SAC
2.16.	Safety (Part A)	EG10	Summary of Maximum QTc Values Post-Baseline Relative to Baseline by Category (Part A)	IDSL	SAC
2.17.	Safety (Part A)	EG2	Summary of Change from Baseline in ECG Values by Visit (Part A)	IDSL	SAC

Safety	Tables				
No.	Population	IDSL / Example Shell	Title	Programming Notes	Deliverable [Priority]
2.18.	Safety (Part A)	EG11	Summary of Maximum Increase in QTc Values Post-Baseline Relative to Baseline by Category (Part A)	IDSL	SAC
Part A	(Cohort 1 – sing	gle ascending dos	se, 3-way crossover): Vital Signs	·	·
2.19.	Safety (Part A)	VS1	Summary of Change from Baseline in Vital Signs (Part A)	ICH E3	SAC
Part A	(Cohort 1 – sing	gle ascending dos	se, 3-way crossover): Suicide Risk Monitoring	·	·
2.20.	Safety (Part A)	CSSRS1	Summary of Subjects with C-SSRS Suicidal Ideation or Behaviour during Treatment (Part A)		SAC
Part B	(Cohorts 2, 3, 4	and 5 – repeat do	ose, sequential-group): Adverse Events (AEs))		
2.21.	Safety (Part B)	AE1	Summary of All Adverse Events by System Organ Class and Preferred Term (Part B)	ICH E3	SAC
2.22.	Safety (Part B)	AE3	Summary of Common (>=10%) Adverse Events by Overall Frequency (Part B)	ICH E3	SAC
2.23.	Safety (Part B)	AE5A	Summary of All Drug-Related Adverse Events by System Organ Class and Preferred Term and Maximum Intensity (Part B)	ICH E3	SAC
2.24.	Safety (Part B)	AE15	Summary of Common (>=10%) Non-serious Adverse Events by System Organ Class and Preferred Term (Number of Subject and Occurrences) (Part B)	FDAAA, EudraCT	SAC
Part B	(Cohorts 2, 3, 4	and 5 – repeat do	se, sequential-group): Serious and Other Significant Adverse I	Events	
2.25.	Safety (Part B)	AE16	Summary of Serious Adverse Events by System Organ Class and Preferred Term (Number of Subjects and Occurrences) (Part B)	FDAAA, EudraCT Only if 3 or more SAEs reported	SAC

Safety:	Tables				
No.	Population	IDSL / Example Shell	Title	Programming Notes	Deliverable [Priority]
2.26.	Safety (Part B)	AE3	Summary of Adverse Events Leading to Permanent Discontinuation of Study Treatment or Withdrawal from Study by Overall Frequency (Part B)	IDSL	SAC
Part B	Cohorts 2, 3, 4	and 5 – repeat do	se, sequential-group): Laboratory: Chemistry		
2.27.	Safety (Part B)	LB1	Summary of Chemistry Changes from Baseline (Part B)	ICH E3	SAC
2.28.	Safety (Part B)	LB17	Summary of Worst Case Chemistry Results by PCI Criteria Post-Baseline Relative to Baseline (Part B)	ICH E3	SAC
2.29.	Safety (Part A)	LB17	Summary of Worst Case Lipids Outside Laboratory Normal Range Post-Baseline Relative to Baseline (Part B)		SAC
Part B	Cohorts 2, 3, 4	and 5 – repeat do	se, sequential-group): Laboratory: Hematology		
2.30.	Safety (Part B)	LB1	Summary of Hematology Changes from Baseline (Part B)	ICH E3	SAC
2.31.	Safety (Part B)	LB17	Summary of Worst Case Hematology Results by PCI Criteria Post-Baseline Relative to Baseline (Part B)	ICH E3	SAC
Part B	Cohorts 2, 3, 4	and 5 – repeat do	se, sequential-group): Laboratory: Urinalysis		
2.32.	Safety (Part B)	UR1	Summary of Worst Case Urinalysis Results (Discrete or Character Values) Post-Baseline Relative to Baseline (Part B)	ICH E3	SAC
Part B	Cohorts 2, 3, 4	and 5 – repeat do	se, sequential-group): Laboratory: Hepatobiliary (Liver)	·	
2.33.	Safety (Part B)	LIVER1	Summary of Liver Monitoring/Stopping Event Reporting (Part B)	IDSL	SAC
2.34.	Safety (Part B)	LIVER10	Summary of Hepatobiliary Laboratory Abnormalities (Part B)	IDSL	SAC

Safety:	Safety: Tables					
No.	Population	IDSL / Example Shell	Title	Programming Notes	Deliverable [Priority]	
Part B	(Cohorts 2, 3, 4	and 5 – repeat do	se, sequential-group): Laboratory: Other			
2.35.	Pharmacoki netic (Part B)	Non-Standard SAFE_T1	Summary of Plasma 4 β -hydroxycholesterol to Cholesterol Ratio (Part B)	Include SE and 95% CI.	SAC	
Part B	(Cohorts 2, 3, 4	and 5 – repeat do	se, sequential-group): ECG			
2.36.	Safety (Part B)	EG1	Summary of ECG Findings (Part B)	IDSL	SAC	
2.37.	Safety (Part B)	EG10	Summary of Maximum QTc Values Post-Baseline Relative to Baseline by Category (Part B)	IDSL	SAC	
2.38.	Safety (Part B)	EG2	Summary of Change from Baseline in ECG Values by Visit (Part B)	IDSL	SAC	
2.39.	Safety (Part B)	EG11	Summary of Maximum Increase in QTc Values Post-Baseline Relative to Baseline by Category (Part B)	IDSL	SAC	
Part B	(Cohorts 2, 3, 4	and 5 – repeat do	se, sequential-group): Vital Signs			
2.40.	Safety (Part B)	VS1	Summary of Change from Baseline in Vital Signs (Part B)	ICH E3	SAC	
Part B	(Cohorts 2, 3, 4	and 5 – repeat do	se, sequential-group): Suicide Risk Monitoring			
2.41.	Safety (Part B)	CSSRS1	Summary of Subjects with C-SSRS Suicidal Ideation or Behaviour during Treatment (Part B)		SAC	

